Eluxadoline is a locally active mixed  $\mu$ OR agonist, kappa-opioid receptor ( $\kappa$ OR) agonist, and delta-opioid receptor ( $\delta$ OR) antagonist approved by FDA on 27 May 2015 for the treatment of IBS-D. Eluxadoline has GI transit-inhibiting activity that is consistent with its primary pharmacological profile as a  $\mu$ OR agonist. The additional  $\delta$ OR antagonist activity may mitigate against the constipating effects of unopposed peripherally acting  $\mu$ OR agonists (e.g., loperamide or diphenoxylate).

Eluxadoline was generally well tolerated in single- and multiple-dose animal studies. Across the Phase 1 studies and Phase 2 study, eluxadoline demonstrated an acceptable safety profile marked by the infrequent incidence of adverse events (AEs) ([Eluxadoline Investigator's Brochure](#)).

Efficacy and safety in IBS-D patients was demonstrated in 2 randomized, multicenter, multi-national, double-blind, placebo-controlled Phase 3 studies in a total of 2426 patients (studies IBS-3001 and IBS-3002; [Lembo et al 2016](#) and [VIBERZI™ PI 2015](#)). The primary endpoint of the Phase 3 trials was defined by the simultaneous improvement in the daily worst abdominal pain (WAP) score by  $\geq 30\%$  compared with baseline weekly average and a reduction in the Bristol Stool Scale (BSS) to  $< 5$  on at least 50% of days within a 12-week treatment period (FDA endpoint) and a 26-week treatment period (European Medicines Agency endpoint). Eluxadoline 100 mg twice daily (BID) demonstrated significantly greater composite responder rates as compared with placebo over 12 weeks and 26 weeks of treatment. Eluxadoline 75 mg BID demonstrated significantly greater responder rates than placebo over 12 weeks in both studies, and greater responder rates than placebo over 26 weeks of treatment in study IBS-3002, but not in study IBS-3001 ([Lembo et al 2016](#), [VIBERZI PI 2015](#)). The treatment effect of eluxadoline over placebo was observed within the first week and was maintained throughout the 26-week assessment period. Based on efficacy of both eluxadoline 75 mg and 100 mg at 12 weeks of treatment, both doses were approved by FDA for treatment of adults with IBS-D.

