### 7.1 Primary Efficacy Endpoints

The primary efficacy endpoint is the proportion of primary composite responders determined over the 12-week double-blind treatment period. A primary composite responder is defined as a patient who meets the daily composite response criteria for at least 50% of days with diary entry during the interval from weeks 1 to 12.

A patient must meet BOTH of the following criteria on a given day to be a daily composite responder:

- Daily pain response: WAP score in the past 24 hours improved by  $\geq 40\%$  compared to baseline pain (average of daily WAP in the week prior to randomization).
- Daily stool consistency response: BSS score  $< 5$  (i.e., score of 1, 2, 3, or 4); or the absence of a bowel movement if accompanied by  $\geq 40\%$  improvement in WAP compared to baseline pain.

To be eligible to be a primary composite responder, a patient must have a minimum of 60 days of diary entries, including partial entries, over the interval from weeks 1 to 12. A partial diary entry consists of any of 3 data components: BSS score, WAP score, and bowel movement frequency. Partial entries will be used to determine whether or not a patient is a daily responder. Any patient with fewer than 60 days of diary entry will be considered a non-primary composite responder, including patients in the ITT analysis who recorded no post-baseline diary data.

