### 7.2 Secondary Efficacy Endpoints

The following are the secondary efficacy endpoints:

- Proportion of stool consistency responders: defined as patients who meet the daily stool consistency response criteria (as defined in Section 7.1) for  $\geq 50\%$  of days with diary entries over a certain time period. This endpoint is defined for the 12-week treatment period, and for each 4-week interval (weeks 1 to 4, 5 to 8, and 9 to 12). For the weeks 1 to 12 time period, the  $\geq 50\%$  requirement is the same as specified for the primary efficacy endpoint in Section 7.1. For each of the 4-week periods, a responder must have a minimum of 20 days of diary entries over the 4 weeks.
- Proportion of pain responders: defined as patients who meet the daily pain response criteria (as defined in Section 7.1) for  $\geq 50\%$  of days with diary entries over a certain time period. This endpoint is defined for the 12-week treatment period, and each 4-week interval (weeks 1 to 4, 5 to 8, and 9 to 12). For the weeks 1 to 12 time period, the  $\geq 50\%$  requirement is the same as specified for the primary efficacy endpoint in Section 7.1. For each of the 4-week periods, a responder must have a minimum of 20 days of diary entries over the 4 weeks.
- Proportion of monthly composite responders: defined as patients who meet the daily composite response criteria (as defined in Section 7.1) for at least 50% of days with diary entry for a minimum of 20 days during each 4-week interval (weeks 1 to 4, 5 to 8, and 9 to 12).

[REDACTED]

[REDACTED]

[REDACTED]

[REDACTED]

[REDACTED]

[REDACTED]

[REDACTED]

[REDACTED]

[REDACTED]

[REDACTED]

[REDACTED]

[REDACTED]

[REDACTED]

[REDACTED]

[REDACTED]

[REDACTED]

[REDACTED]

[REDACTED]

[REDACTED]

[REDACTED]

[REDACTED]

[REDACTED]

[REDACTED]

[REDACTED]

[REDACTED]

[REDACTED]

[REDACTED]

[REDACTED]

[REDACTED]

[REDACTED]

[REDACTED]

[REDACTED]

[REDACTED]

[REDACTED]

[REDACTED]

[REDACTED]

[REDACTED]

[REDACTED]

[REDACTED]

[REDACTED]

[REDACTED]

[REDACTED]

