5. Duration to Study Treatment(s) and Compliance of Treatment.....	11

6.3 Primary Efficacy Analyses	14
-------------------------------------	----

6.3.1 Primary Analyses for Primary Efficacy Endpoint.....	15
---	----

[figure not shown]
6.3.2 Other Analysis for Primary Efficacy Endpoint 15
6.4 Secondary Efficacy Analyses 15

8. Interim Analyses 22
9. Deviations from Protocol 22
10. Appendices 24

10.2 Bristol Stool Scale 28

11. Signature Page 70

1. Introduction

The analyses described in the SAP are based upon the final protocol dated 12 August 2016. Where differences exist between analyses specified in the protocol and this SAP, the SAP will be followed.

This is a Phase 4, multicenter, multinational, randomized, double-blind, placebo-controlled, parallel group study to evaluate the efficacy, safety, and tolerability of eluxadoline 100 mg BID in patients with IBS-D who report that use of loperamide to treat their IBS-D symptoms in the prior 12 months failed to adequately control their symptoms of IBS-D. (RELIEF)

Approximately 340 patients will be randomly assigned (in a 1:1 ratio) to 1 of 2 treatment groups below:

- Group 1: eluxadoline 100 mg oral tablets BID with food
- Group 2: matching placebo oral tablets BID with food

During the screening period (up to 1 week), screening procedures, including Prior Symptoms Management Questionnaire (refer to Appendix 10.7), will be performed. After that, eligible patients will enter a pretreatment period (up to 3 weeks). At the beginning of the pretreatment period, patients will receive instructions for completing an electronic patient-reported outcome (ePRO) diary to collect daily information related to their IBS-D symptoms and use of loperamide rescue medication. At the end of the pretreatment period, patients who meet the study inclusion criteria related to ePRO diary compliance, stool consistency (Bristol Stool Scale [BSS]), average worst abdominal pain (WAP) score, and use of loperamide rescue medication will be randomized into a 12-week double-blind treatment period via central randomization.

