6.4 Secondary Efficacy Analyses

[figure not shown]
The following are the secondary efficacy endpoints:

- Proportion of stool consistency responders: defined as patients who meet the daily stool consistency response criteria (BSS <5, or absence of a bowel movement) for $\geq 50\%$ of days with diary entries over a certain time period. This endpoint is defined for the 12-week treatment period and for each 4-week interval (week 1 to 4, 5 to 8, and 9 to 12). For the 12-week treatment period, the $\geq 50\%$ requirement is the same as specified for the primary efficacy endpoint in Section 6.3. For each of the 4-week intervals, a responder must have a minimum of 20 days of diary entries over the 4 weeks. Any patient with fewer than 60 days (for 12-week period) or with fewer than 20 days (for 4-week interval) of diary entries will be considered as a non-responder.

- Proportion of pain responders: defined as patients who meet the daily pain response criteria (as defined in Section 6.3) for $\geq 50\%$ of days with diary entries over a certain time period. This endpoint is defined for the 12-week treatment period and for each 4-week interval (week 1 to 4, 5 to 8, and 9 to 12). For the 12-week treatment period, the $\geq 50\%$ requirement is the same as specified for the primary efficacy endpoint in Section 6.3. For each of the 4-week intervals, a responder must have a minimum of 20 days of diary entries over the 4 weeks. Any patient with fewer than 60 days (for 12-week period) or with fewer than 20 days (for 4-week interval) of diary entries will be considered as a non-responder.
- Proportion of monthly composite responders: defined as patients who meet the daily composite response criteria (as defined in Section 6.3) for at least 50% of days with diary entry for each 4-week interval (week 1 to 4, 5 to 8, and 9 to 12). For each of the 4-week intervals, a responder must have a minimum of 20 days of diary entries over the 4 weeks. Any patient with fewer than 20 days of diary entries for the 4-week interval will be considered as a non-responder.

The secondary endpoints will be analyzed by the number and percentage of the corresponding responders with p-value from chi-square test to test the different response rates between treatment groups. No adjustment for the multiplicity of the endpoints will be performed.

[figure not shown]

[figure not shown]
8. Interim Analyses

[figure not shown]
There will be no interim analysis for this study.

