9. Deviations from Protocol

[figure not shown]
This analysis mentioned in protocol section [7.7.3](#), “The mixed-effect model for repeated measures method will be used to analyze these endpoints with treatment group as the factor and baseline endpoint values as covariate.” is not performed.

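### SAP Section 6.4 counts every day without a bowel movement as a stool-consistency response; the protocol and SAP Section 6.3 count it only with at least 40% pain improvement

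*SAP*

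**What the plan says.** Protocol Section 7.1 accepts a day as a stool-consistency response if BSS is below 5, "or the absence of a bowel movement if accompanied by" an improvement in WAP of at least 40% from baseline. Protocol Section 7.2 carries that rule into the secondary endpoint by cross-reference: stool responders are "defined as patients who meet the daily stool consistency response criteria (as defined in Section 7.1) for" at least half of diary days, over weeks 1 to 12 and in each 4-week interval.

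SAP Section 6.3 repeats the protocol's daily rule, pain condition included, for the primary endpoint. SAP Section 6.4 then writes out a different rule for the secondary endpoint. Its stool responders are those who "meet the daily stool consistency response criteria (BSS <5, or absence of a bowel movement"), with no pain condition. The pain bullet beside it does use the cross-reference ("defined as patients who meet the daily pain response criteria (as defined in Section 6.3) for" at least half of days), and so does the monthly composite bullet.

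SAP Section 1 settles precedence: "Where differences exist between analyses specified in the protocol and this SAP, the SAP will be followed". The visible text of SAP Section 9 lists one deviation, the dropped repeated-measures analysis ("The mixed-effect model for repeated measures method will be used to analyze these endpoints with treatment group as the factor"), and does not mention the stool criterion.

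**The concern.** The same term, daily stool consistency response, has two definitions within the SAP, and the one attached to the secondary endpoint is not the protocol's. Because the SAP takes precedence, a programmer following Section 6.4 would code the unconditional rule.

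Under that rule an absent stool is a success even on a day when pain has not improved. Protocol Section 6.3.2.1 treats 4 consecutive days without a bowel movement as diary-confirmed constipation; all 4 would score as stool-consistency responses. Protocol Section 1 states that "Eluxadoline has GI transit-inhibiting activity that is consistent with its primary pharmacological profile". If the active arm has more days without a bowel movement, some of any stool-responder difference would come from those days rather than from better stool form.

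The endpoint is tested without protection: "No adjustment for the multiplicity of the endpoints will be performed". The secondary tests number 11 (stool 4, pain 4, monthly composite 3), and 4 of them use the changed rule.

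**Working it through.** **Step 1. The definitions side by side**

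| Place | Day with a bowel movement | Day without a bowel movement |
|---|---|---|
| Protocol 7.1, used by 7.2 | BSS < 5 | counts only if WAP improved ≥40% |
| SAP 6.3 | BSS < 5 | counts only if WAP improved ≥40% |
| SAP 6.4, stool bullet | BSS < 5 | always counts |

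The composites are untouched. A composite day needs the pain response anyway, so on a day without a bowel movement both rules give the same composite result.

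**Step 2. The plan's own figures.** The documents give no sample size or power for the stool endpoint. The stated design concerns the primary endpoint and is not at issue: 13% against 27%, two-sided 0.05, uncorrected chi-square gives 170 per arm, and the power at 170 is 90.1%.

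**Step 3. Shift in the effective threshold (exact).** Let *n* be a patient's share of diary days without a bowel movement, with no ≥40% pain improvement on any of them. The share of bowel-movement days that must have BSS < 5 for the patient to respond is:

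- protocol rule: 0.5 / (1 − n)
- SAP 6.4 rule: (0.5 − n) / (1 − n)

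At n = 10%: 0.5/0.9 = 55.6% against 0.4/0.9 = 44.4%. At n = 15%: 0.5/0.85 = 58.8% against 0.35/0.85 = 41.2%.

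**Step 4. One patient, with assumed counts.** Of 84 diary days, 30 have BSS < 5 and 14 have no bowel movement; 2 of those 14 have ≥40% pain improvement. Protocol rule: (30 + 2)/84 = 38.1%, a non-responder. SAP 6.4: (30 + 14)/84 = 52.4%, a responder.

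**Step 5. Possible size between arms (simulation; every input is an assumption).** 200,000 patients per arm and 84 days, with independent beta-distributed patient probabilities. Mean share of BSS < 5 on bowel-movement days is 30, 35 or 40% (concentration 2, 3 or 6), the same in both arms, so there is no drug effect on stool form. Days without a bowel movement average 5% on placebo and 5, 10 or 15% on active (concentration 4, 8 or 20). Pain-response days average 35% on placebo and 35 or 50% on active (concentration 2). Ranges are the minimum and maximum over the 27 settings, for active minus placebo in percentage points.

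| Days without a bowel movement, placebo vs active | SAP 6.4 | Protocol rule, equal pain response | Protocol rule, pain response 35% vs 50% |
|---|---|---|---|
| 5% vs 5% | about 0 | about 0 | about +0.3 to +1.7 |
| 5% vs 10% | +2.6 to +6.1 | −1.5 to −0.3 | +0.8 to +2.0 |
| 5% vs 15% | +6.2 to +12.4 | −2.2 to −0.6 | +1.0 to +3.0 |

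Repeat runs agree for SAP 6.4 to within sampling error; the protocol-rule limits move by up to about 0.5 point. With 5% of such days, SAP 6.4 raises the response level by about 2.8 to 6.7 points over the grid (for example from 27.4% to 31.8% at mean 35%, concentrations 3 and 8). Days without a bowel movement alone reach half of all days (42 of 84) in about 0 to 5% of simulated patients, so the effect comes mainly from patients near the threshold.

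**The case against.** The strongest reply is that the change may be deliberate and sensible. The protocol synopsis, under Statistical Methods, describes the secondary comparison as pain or stool consistency on its own, and a rule that uses pain to score a stool day does not quite fit that. The pain condition is redundant in the composite and has an effect only in the stool endpoint. It can also carry a pain benefit into a stool endpoint: with equal days without a bowel movement and better pain response on active, the protocol rule shows about +0.3 to +1.7 points with no stool effect, where SAP 6.4 shows none. This stands as an argument about which rule is preferable. It does not remove the mismatch, because Protocol Section 7.2 points explicitly to Section 7.1.

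Non-declaration cannot be proved either. Parts of SAP Section 9, and the text between Sections 6.4 and 8, are not shown. That stands; only the visible text can be judged.

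The simulated differences assume that days without a bowel movement double or triple while stool form stays the same, which is a strained combination for a drug that slows transit. Protocol Section 1 also says that delta-receptor antagonism may offset constipation, and Section 5.9 allows rescue loperamide in both arms. The figures therefore show a mechanism, not an expected size.

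Finally, the endpoint is secondary and outside any testing hierarchy. That limits the consequence but not the need to reconcile the text.

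**Conclusion.** The concern holds. SAP Section 6.4 defines a stool-responder endpoint that is not the one in Protocol Section 7.2, and the precedence clause makes the SAP version operative. This rests on the text alone.

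The direction at patient level is also certain: the SAP rule never removes a response day and can only add them. How much it adds depends on the unreported frequency of days without a bowel movement and on pain on those days. A bias between arms is conditional on the arms differing in such days. Under the assumptions above it could range from nothing to about 12 points, and the protocol rule is not neutral either. Four unadjusted secondary tests are affected; the primary analysis, the monthly composites and the sample size are not. This should be fixed, but it does not threaten the trial's main conclusion.

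**What to change.** In SAP Section 6.4, replace the parenthesis in the stool bullet with *(as defined in Section 6.3)*, which matches Protocol Section 7.2 and the two neighbouring bullets. If the unconditional rule is wanted, declare and justify it in SAP Section 9 and report it as a labelled sensitivity analysis beside the protocol's definition.

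In either case, tabulate by arm the share of diary days without a bowel movement, unless a section not shown already does so, so that readers can see how much of any stool difference comes from those days.

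The cost is one line of SAP text, one derivation and one descriptive table from diary data already collected. The reported stool-responder rates may come out somewhat lower.

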10.2 Bristol Stool Scale

Type 1 - Separate hard lumps like nuts (difficult to pass)

Type 2 - Sausage shaped but lumpy

[figure not shown]
Type 3 - Like a sausage but with cracks on surface

[figure not shown]
Type 4 - Like a sausage or snake, smooth and soft

[figure not shown]
Type 5 - Soft blobs with clear-cut edges (passed easily)

[figure not shown]
Type 6 - Fluffy pieces with ragged edges, a mushy stool

[figure not shown]
Type 7 - Watery, no solid pieces (entirely liquid)

[figure not shown]

[figure not shown]

[figure not shown]

[figure not shown]

[figure not shown]

[figure not shown]

[figure not shown]

[figure not shown]

[figure not shown]

[figure not shown]

[figure not shown]

[figure not shown]

[figure not shown]

[figure not shown]

[figure not shown]

[figure not shown]

[figure not shown]

[figure not shown]

[figure not shown]

[figure not shown]

[figure not shown]

[figure not shown]

[figure not shown]

[figure not shown]

[figure not shown]

[figure not shown]

[figure not shown]

[figure not shown]

[figure not shown]

[figure not shown]

11. Signature Page

Study ID: CMO-US-GI-0429

Version: 1.0

Issue Date: October 18, 2017
